4.3 Primary Objective: All-cause mortality and intervention for heart failure decompensation

The primary objective is to test the hypothesis that aCRT reduces the incidence of the combined endpoint of all-cause mortality and intervention for heart failure decompensation, compared to standard CRT therapy, in patients with a CRT indication, LBBB and normal AV conduction.

4.3.1 Hypothesis

The null hypothesis is that the hazard ratio for treatment (aCRT ON) versus control (aCRT OFF) is equal to 1. It will be tested against the alternative hypothesis that the hazard ratio is unequal to 1.

Let $S_T(t)$ and $S_C(t)$ denote the proportion of patients in the treatment arm and control arm, respectively, that have not experienced a primary endpoint up to time t . Let $h_T(t)$ and $h_C(t)$ be the associated hazard functions. Under the proportional hazards model, $h_T(t) = HR \cdot h_C(t)$, where HR is the hazard ratio of treatment compared to control. The null and alternative hypotheses can be expressed as:

$$H_0 : HR = 1$$

$$H_A : HR \neq 1$$

Endpoint Definition

The primary endpoint is the composite of all-cause death and any intervention for heart failure decompensation (HF event) as adjudicated by the EAC. Intervention of heart failure decompensation is defined as an event that requires "invasive intervention (i.e. IV diuretics, ultrafiltration, or equivalent) or inpatient hospitalization".

The EAC will determine if an endpoint has been met. Sites may adhere to their standard practice diagnosing heart failure, but are required to report all diagnostic assessments, tests and procedures done with supporting material as appropriate to allow the EAC to adjudicate.

The analysis will use time to event in study for each subject, defined from the date of randomization (per randomization form) to date of last follow-up or date of primary event, whichever is first. The date of the event will be the date of death or the date of initiation of treatment for heart failure decompensation as determined by the EAC. Subjects without

primary event will be followed up until study closure. Subject deaths and HF events will be collected on case report forms. Any events that occur before the date of randomization will not be included in the intent-to-treat analysis. If a subject has more than one event that contributes to the primary endpoint, the first of these events will be used in the test statistic.

The study will be event driven, based on the number of patients that experienced an event. The study will continue until a predetermined number of events have been observed, unless the DMC advises to stop earlier.

4.3.2 Analysis Methods

The hypothesis will be tested using a Cox proportional hazards regression model with a random site effect (frailty), stratified by NYHA class at enrollment. In this combination of stratified Cox regression and frailty model, the hazard for subject i from site j with NYHA class k at enrollment is:

$$\lambda_{ijk}(t) = \lambda_{0k}(t) \xi_j \exp(\beta X_{ijk})$$

where $i = 1, \dots, n$; $j = 1, \dots, J$; $k = 1, 2, 3$.

$\lambda_{0k}(t)$ is the baseline hazard of k^{th} NYHA class. This is the part of stratified Cox regression, where the baseline hazards of NYHA class play no role in the estimation of treatment effect. That is, no between-NYHA-class comparisons of treatment effect are attempted and all information about the treatment effect comes from within NYHA class comparisons. ξ_j ($j = 1, \dots, J$) are frailties or site effects that follow a gamma distribution with mean 1 and variance θ_0 independently and identically. The variance parameter θ_0 is a measure of the heterogeneity across sites in baseline risk. As θ_0 increases, the values of ξ_j become more dispersed, inducing greater heterogeneity in the site-specific baseline hazards. This is the part of random effects or frailty model.⁷ Therefore, $\xi_j \lambda_{0k}(t)$ is the baseline hazard of k^{th} NYHA class at j^{th} site, and ξ_j is constant for $k = 1, 2, 3$ NYHA class from the same site j . X_{ijk} is the randomization assignment (ACRT ON or ACRT OFF), and $\exp(\beta)$ is the hazard ratio for treatment.

The SAS PHREG procedure will be used to conduct the survival analysis of primary endpoint using code similar to:

```
PROC PHREG DATA=primary;
  CLASS NYHA site;
  MODEL time*event(0) = rand / TIES=efron;
  STRATA NYHA;
  RANDOM site/ dist = gamma;
RUN;
```

Event = 1 when a subject experienced an event that was adjudicated as primary endpoint (intervention for HF decompensation or death). Event = 0 when a subject did not experience a primary endpoint, and therefore was censored. Time to event starts from the date of randomization and ends at the date that the event occurs for those who experience

the event or the date of last documented follow-up since randomization for those who are censored. Date of last documented follow-up since randomization is the maximum value among the dates of randomization, randomization programming, any study scheduled follow-up visit, exit, adverse event onset, adverse event resolved, system modification, and healthcare utilization. Rand is an indicator variable for randomized treatment groups (1=aCRT ON, 0=aCRT OFF).

The hazard ratio for treatment arm (aCRT ON) versus control arm (aCRT OFF) will be reported with its associated p-value and 95% confidence interval. The null hypothesis will be rejected when the p-value is below the critical value for the (interim or final) analysis. The actual cumulative α level will be calculated based on the actual number of primary events included in each interim analysis. The estimated cumulative α -level is approximately 0.00002, 0.00304, 0.0193 and 0.05 at the 1st interim with 275 events, 2nd interim with 550 events, 3rd interim with 825 events and the final analysis with 1100 events, respectively (see details in section 0). It will be concluded that aCRT reduces the incidence of the primary endpoint when the null-hypothesis is rejected and the hazard ratio is below 1. Kaplan-Meier plots for incidence of primary endpoint will be presented by treatment arms, for all patients and for the separate NYHA class groups. The absolute event rate difference at 2 years post randomization will also be calculated.

The following model assumptions will be checked:

1. Proportional hazards between treatment arms: an interaction term of treatment arm by time (in log scale) will be added into the model (see the code below). If this interaction effect is not significant, the proportional hazard assumption holds. Otherwise, this interaction term should be kept in the model as a remedy for non-proportional hazards, and any secondary analysis where treatment (or treatment by subgroup factor interaction) is included should also include the corresponding interaction term with time. Being time dependent, the treatment effect will be assessed every 6 months to the end of the follow-up to monitor the direction. Significance of the treatment effect will be based on its estimate at 24 months using a contrast.

```
PROC PHREG DATA=primary;  
  CLASS NYHA site;  
  MODEL time*event(0) = rand rand_t / TIES=efron;  
  rand_t = rand*log(time);  
  STRATA NYHA;  
  RANDOM site/ dist = gamma;  
RUN;
```

2. Hazard ratio for treatment is constant across NYHA classes: the following code will be used to check this assumption. That is, instead of doing stratified Cox regression, NYHA class will be regarded as a covariate in a frailty model along with the interaction between treatment and NYHA class. If the interaction is not significant and the hazard ratios for treatment are similar at different NYHA classes, the assumption of stratified Cox regression part of the model in primary analysis is valid. If the interaction is significant, the assumption does not hold, and we will consider NYHA class as a covariate instead of a stratification factor in the frailty model for primary analysis and other relevant analyses, and keep the interaction term in the model. The treatment effect will be reported separately for the different NYHA classes.

```
PROC PHREG DATA=primary;  
  CLASS NYHA(ref='NYHA class II') site rand(ref=0)
```

```
        / param=ref order=internal;  
MODEL time*event(0) = rand NYHA rand*NYHA / TIES=efron;  
RANDOM site/ dist = gamma;  
HAZARDRATIO rand / diff=all at (NYHA='NYHA class II');  
HAZARDRATIO rand / diff=all at (NYHA='NYHA class III');  
HAZARDRATIO rand / diff=all at (NYHA='NYHA class IV');  
RUN;
```

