11.3.4 Sample size rationale

A total of 1100 patients experiencing a primary endpoint will give 90% power to show a significant reduction of the incidence of the primary endpoint, accounting for 3 equally spaced interim analyses and assuming a true intent-to-treat hazard ratio of 0.82 for aCRT ON compared to aCRT OFF.

Version 1.0 of the CIP specified the total number of patients randomized as follows: With the inclusion of 2874 randomized patients enrolled over 3 years and followed for 2.3 more years, 1100 primary endpoint events are expected when the true control arm event-free rate is 75% at 2 years.

Version 2.0 of the CIP increases the total number of patients randomized to accommodate a lower event rate: With the inclusion of 3326 randomized patients enrolled over 4 years and followed for 3.5 more years, 1100 primary endpoint events are expected when the true control arm event-free rate is 85% at 2 years.

The study will randomize approximately 3500 patients in order to accommodate attrition due to early exit. The study will be event-driven and the DMC may advise to stop enrollment early when the primary endpoint rate is higher than expected.

Through simulation it was confirmed for version 1.0 of the CIP that the study will have 90% power under the following assumptions:

- 3000 patients randomized in 3 years with a uniform rate

[figure not shown]
- control arm event-free rate is 75% at 2 years
- LBBB is not confirmed by the ECG Core Laboratory in 10% of patients
- aCRT hazard ratio is 0.78 in confirmed LBBB patients, 1.0 in unconfirmed patients
- crossover rate is 5% at 2 years in aCRT arm and 8% at 2 years in control arm
- loss-to-follow-up rate is 5% at 2 years in both arms
- final analysis is done when 1100 events are accrued

For version 2.0 of the CIP, the simulation was updated and the power of 90% was confirmed with updated control group event rate expectation.

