4 DESCRIPTION OF ANALYSIS

4.1 General

Medtronic employed statisticians will perform the statistical analyses described in this SAP. Interim analyses will be performed by a Medtronic statistician other than the lead statistician for the study. The lead study statistician will be blinded to all interim analyses.

All tests of treatment effects will be conducted in order to preserve an overall two-sided alpha level of 0.05 unless otherwise stated. An Intention-to-Treat analysis will be performed and will serve as the primary analysis for all objectives in this study. The Intention-to-Treat cohort will include all randomized subjects.

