4.3.6 Ancillary Analysis: Covariate Adjustment and Risk Score

Subject characteristics at enrollment and baseline will be considered as covariates in an ancillary analysis. The purpose is to verify the treatment effect controlling for covariates. The ancillary analysis may only be conducted for the final report.

The subject characteristics include: from enrollment visit, gender, PR interval, QRS duration, and LVEF; from baseline form, age, physical exam status, cardiac disease classification, current HF symptoms, blood measurements, and medical history at baseline (section 4.1.1). NYHA class at enrollment will be regarded as a covariate instead, which means the corresponding model will no longer have the component for stratified Cox regression.

First, the effect of each subject characteristic on the primary endpoint will be estimated in a univariate model as follows:

```
PROC PHREG DATA=primary;
  CLASS site SubjCha; * CLASS only if SubjCha is categorical;
  MODEL time*event(0) = SubjCha / TIES=efron;
  RANDOM site/dist = gamma;
RUN;
```

Again, in this SAS PHREG procedure, event = 1 when a subject experiences a primary endpoint and event = 0 otherwise; and time to event starts from the date of randomization and ends at the date that the first event occurs for those who experience the event or the date of last documented follow-up since randomization for those who are censored; SubjCha is a specific baseline characteristic of interest.

Next, the subject characteristics that are significant in a univariate model will be included in a full model and backwards selection method will be used to determine significant predictors. After that, the treatment factor will be added into the model along with the interaction terms between treatment and possible effect modifiers such as gender, ECG Core Lab confirmed LBBB, AV conduction time, QRS, NYHA class at enrollment and MI. Backwards selection will be used to eliminate the interaction terms that are not significant. If an interaction is significant, the relevant subject characteristics need to remain in the model regardless whether their single effects being significant or not. Note the backwards selection will be performed manually because the SAS PHREG procedure ignores the SELECTION option for the frailty model analysis.

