Based on the literatures^{8,9}, the following characteristics are expected in the final model: from enrollment form, gender, QRS duration, ECG Core Lab confirmed LBBB, LVEF, NYHA class, AV conduction time; from baseline form, age, BMI, SBP, rales/crackles, dyspnea, peripheral edema, HF admissions in past 6 months, creatinine, history of MI, AF, diabetes and smoking; from cardiovascular medication log, baseline diuretics dose, and ACE/ARB. If not, we might consider to add them into the final model in order to compare with the literature.

A risk score for the primary endpoint can be defined as $\mathbf{X}\beta$ with \mathbf{X} being the covariates remained in the final model.

The critical values for the treatment effect in the primary analysis (estimated cumulative α -level of approximately 0.00002, 0.00304, 0.0193 and 0.05 at the 1st, 2nd, 3rd interim and the final analysis, respectively) will not be applied to this ancillary analysis.

Multiple imputation will be used to handle missing values for the covariates in the multi-variable models. The SAS MI and MIANALYZE procedures will be used to conduct multiple imputation.

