The required number of HF event or death to get 90% overall study power is estimated using the following SAS SEQDESIGN procedure (also Section 5.1):

```
proc seqdesign
  boundaryscale=stdz
  errspend
  stopprob
  plots=boundary(hscale=samplesize);
;
Interim: design
  alpha = 0.05
  alt = twosided
  beta = 0.10
  stop = both
  nstages = 4
  method = errfuncobf
;
samplesize
  model = twosamplesurv
  ( nullhazard = 0.14384
    hazardratio = 0.81818
    acctime = 3.0
    foltime = 2.25
  );
run;
```

that assumes:

- Type I error rate: 0.05
- Type II error rate: 0.10, which corresponds to 90% power
- 3 equally spaced interim analyses plus the final analysis
- Hazard of aCRT OFF arm: 0.14384
- Hazard ratio of aCRT: 0.81818
- Enrollment duration: 3 years
- Follow-up duration: 2.25 years

The results (Section 5.1) show that a total of 1100 patients experiencing a primary endpoint will give 90% power to detect a reduction of the incidence of the primary endpoint at a significance level of 0.05, accounting for 3 equally spaced interim analyses and assuming a true intent-to-treat hazard ratio of 0.82 for aCRT ON compared to aCRT OFF.

With the inclusion of 2874 randomized patients enrolled over 3 years and followed for 2.3 years, 1100 events are expected when the true event-free rate of aCRT OFF arm is 75% at 2 years.

The study will randomize up to 3000 patients in order to accommodate attrition due to early exit and to accommodate the possibility of a somewhat lower control arm event rate. Through simulation (Section 1.1) it was confirmed that the study will have 90% power under the following assumptions:

- 3000 patients randomized in 3 years with a uniform rate
- Event-free rate of aCRT OFF arm is 75% at 2 years
- LBBB is not confirmed by the ECG Core Lab in 10% of patients
- aCRT hazard ratio is 0.78 in confirmed LBBB patients and 1.0 in unconfirmed patients
- Crossover rate at 2 years is 5% in aCRT ON arm and 8% in aCRT OFF arm
- Loss to follow-up rate is 5% at 2 years in each arm
- Final analysis is done when 1100 primary events are accrued

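### The primary Cox model uses none of the baseline predictors that the SAP already names, beyond NYHA class and site: missed efficiency, not an error in the 1100-event design

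*SAP*

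**What the plan says.** SAP 4.3.2 tests the primary hypothesis with a "Cox proportional hazards regression model with a random site effect (frailty), stratified by NYHA class at enrollment". The accompanying code has treatment as the only term in the model statement. Protocol 11.3.2 specifies the same model.

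All other baseline adjustment is ancillary (SAP 4.1.2.4, 4.1.2.5 and 4.3.6). Under 4.3.6, each characteristic is screened in a univariate model. Those that are significant enter a full model, and "backwards selection method will be used to determine significant predictors". Treatment is added next, together with candidate interactions that are again eliminated by significance.

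The same section then states, citing literature, that "the following characteristics are expected in the final model". It lists sex, QRS duration, core-laboratory LBBB, LVEF, NYHA class, AV conduction time, age, BMI, systolic blood pressure, signs of heart failure, heart failure admissions in the past 6 months, creatinine, history of MI, AF, diabetes, smoking and medication. Listed items that are not selected might be added back. The risk score is whatever linear predictor remains in the final model.

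Protocol 11.3.2 plans a risk-score Cox model as a further analysis but does not define the score. SAP 4.3.6 and Table 2 place the adjusted analysis in the final report only.

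**The concern.** In a Cox model, leaving out prognostic covariates pulls the treatment hazard ratio towards 1 and costs power, even under perfect randomization. Wanting a purely marginal hazard ratio is not a strong reason to leave them out here, because the model already conditions on NYHA class and site.

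Events are the scarce resource in this trial. Protocol 11.3.4 and its change history record an increase from 3000 to about 3500 randomized patients and a longer study, after the assumed 2-year control event-free rate moved from 75% to 85%. Covariates fixed in advance recover part of that resource without more patients or follow-up.

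The ancillary model does not fill the gap. Its covariates, interactions and risk score are all settled by the trial's own outcomes. If an interaction is retained, there may be no single adjusted treatment effect to report.

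**Working it through.** **Inputs from the documents**
- Error rate (SAP 4.1): "All tests of treatment effects will be conducted in order to preserve an overall two-sided alpha level of 0.05 unless otherwise stated".
- Power (SAP 4.3.8): "Type II error rate: 0.10, which corresponds to 90% power".
- Effect (SAP 4.3.8): "Hazard ratio of aCRT: 0.81818", rounded to 0.82 in the text.
- Looks (SAP 4.3.8): "3 equally spaced interim analyses plus the final analysis", with efficacy and futility boundaries in the code.
- Events (Protocol 11.3.4): "A total of 1100 patients experiencing a primary endpoint will give 90% power to show a significant reduction".
- Size and timing (Protocol 11.3.4): 3326 patients, 4 years of accrual plus 3.5 years, 85% of controls event-free at 2 years.

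**Input not in the documents.** The prognostic strength of the omitted covariates beyond NYHA class and site. I assume a normally distributed baseline score with log-hazard SD of 0.3, 0.5 or 0.7. The hazard ratio between patients one SD above and one SD below the mean is exp(2 × SD), which is 1.8, 2.7 or 4.1.

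**Step 1: reproduce the plan's figure.**
- Fixed design: D = 4(1.960 + 1.282)² / (ln HR)² = 42.03 / (ln HR)². With ln 0.81818 = −0.2007, D = 1044. With HR 0.82, D = 1068.
- Four equally spaced looks at the stated cumulative levels (0.00002, 0.00304, 0.0193, 0.05), efficacy bounds only: inflation 1.023, giving 1067 events.
- With futility bounds as in the SAP code: inflation 1.056, giving 1103 events.

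The stated 1100 is confirmed. The calculation is a two-sample log-rank one without covariates, so 0.82 is an unadjusted hazard ratio.

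**Step 2: the same trial with and without adjustment.** I simulated 2000 trials per setting: 3326 patients, analysis at event 1100, 85% of controls event-free at 2 years, no crossover or loss. The conditional hazard ratio was set so that the unadjusted one is 0.82. Each trial was fitted with treatment alone and with treatment plus the score. Power is Φ(mean Z − 1.96) at a single look. As a check, the expected unadjusted Z is (√1100 / 2) × |ln 0.82| = 16.58 × 0.1985 = 3.29; the simulated values are 3.26 to 3.28.

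| Score SD | Conditional HR | Mean Z unadjusted / adjusted | Ratio of Z² | Power unadjusted / adjusted | Events for the unadjusted power |
|---|---|---|---|---|---|
| 0.3 | 0.817 | 3.28 / 3.33 | 1.032 | 90.7% / 91.5% | 1100 / 1.032 = 1066 (3% fewer) |
| 0.5 | 0.812 | 3.28 / 3.45 | 1.104 | 90.7% / 93.2% | 1100 / 1.104 = 997 (9% fewer) |
| 0.7 | 0.804 | 3.26 / 3.60 | 1.217 | 90.3% / 94.9% | 1100 / 1.217 = 904 (18% fewer) |

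The fitted score is the true one, so these gains are upper bounds. A real covariate list would capture only part of it.

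**The case against.** **No shortfall against the design.** A reader might infer that the trial is underpowered. If 0.82 were the covariate-conditional hazard ratio, the unadjusted one would drift to 0.822, 0.828 or 0.835, and unadjusted power would be 90.0%, 87.5% or 84.8% at SD 0.3, 0.5 or 0.7. The documents do not assume that. They call 0.82 the true intent-to-treat hazard ratio and size the trial without covariates. This objection stands in full.

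**Strength is unknown.** Nothing in the documents shows that the omitted covariates are strong, and NYHA class and site already absorb some prognosis. At SD 0.3 the gain is only about 1 power point. The shift from 0.67 to 0.76 after adjustment in the earlier study's post-hoc subgroup (SAP 4.3.8) is no guide, because it may reflect confounding or chance imbalance. This stands, and is why the size is given as a range.

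**Missing data.** Protocol 6.6 collects blood values only when they are standard of care, so creatinine could be missing often and unevenly by site. The multiple imputation planned in SAP 4.3.6 serves the ancillary models, not the confirmatory test. This stands, and removes creatinine from the list.

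**The selection is less data-driven than it looks.** Main effects are chosen before treatment enters, so that step cannot be tuned to the treatment effect, and literature predictors may be added back. This stands in part: the covariate set, the interactions and the score still depend on the trial's outcomes, and adding back is optional.

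**Cost and timing.** The model is also fixed in Protocol 11.3.2. From the proposed start of June 2014, looks at 3.5, 5.0 and 6.5 years fall at about December 2017, June 2019 and December 2020, all before SAP version 3.0 of 15 November 2021. The documents do not say whether they took place. If they did, a new model at the final look would mix test statistics within one alpha-spending plan. This stands, and governs the fix.

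**Analysing by the randomization strata is valid.** It is, and accepting NYHA class and site does not oblige the sponsor to add more covariates. It does weaken the argument for leaving them out.

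**Conclusion.** The concern holds as missed efficiency. The primary analysis is valid, and its 1100 events and 90% power are confirmed for an unadjusted hazard ratio of 0.82. With a fixed covariate set, power at 1100 events would rise from about 90–91% to about 91.5–95%, or about 3–18% fewer events would give the same power. This rests on an assumed log-hazard SD of 0.3 to 0.7 beyond NYHA class and site, and on a known score, so it is an upper bound. From the documents alone, only the direction is certain.

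Separately, the planned adjusted analysis should not have its covariates and risk score defined by the trial's own outcomes when the SAP can already name them.

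**What to change.** **If no interim look has yet used the unadjusted model:** the blinded lead statistician pre-specifies, in both Protocol 11.3.2 and SAP 4.3.2, a short fixed list of required baseline items drawn from SAP 4.3.6. An example is age, sex, LVEF, QRS duration, systolic blood pressure, heart failure admission in the past 6 months, diabetes and history of MI. Creatinine is left out. NYHA strata and site frailty stay. The text should state that the conditional hazard ratio is primary, give a simple rule for missing covariate values, and keep the current model as a sensitivity analysis.

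**If looks have already used it,** as the planned calendar suggests: keep the unadjusted model as the primary test. Fix the same list for the planned adjusted and risk-score analysis, in place of the univariate screening and backward selection in SAP 4.3.6.

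**Cost:** no extra patients, visits or data. The first route gives a hazard ratio slightly further from 1 (for example 0.81 against 0.82 at SD 0.5), some handling of missing covariates, and a protocol alignment. If the SAP alone changed, Protocol 11.1 would require the departure to be explained in the Final Report. The second route is a change to SAP wording.
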